### 4. STATISTICAL ANALYSES

### 4.1. General Considerations

### 4.1.1. General Methodology

The Safety Analysis Set will be used for all study population, efficacy, and safety analyses, unless otherwise specified. AE and PK related tables, listings and figures will be summarized by dose level. Study population and efficacy tables and listings will be summarized by treatment sequence.

The DLT-evaluable Analysis Set will be used for assessment of dose-limiting toxicities.

Confidence intervals will use 95% confidence levels unless otherwise specified.

Unless otherwise specified, continuous data will be summarized using descriptive statistics: n, mean, standard deviation (std), median, minimum, and maximum. Categorical data will be summarized as the number and percentage of participants in each category.

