# **Overall Design and Brief Summary:**

This is a Phase 1, open label, dose escalation study to evaluate safety, pharmacokinetics, and pharmacodynamics of intravenous GSK3745417 in participants with relapsed or refractory AML or high risk MDS.

The study will be conducted in a staged approach consisting of 2 parts. Part 1 will evaluate a dosing schedule of a 5 days on/2 days off schedule for 2 weeks, and then have an additional 2 weeks off dose for observation for a total of 28 days in each cycle (5/2)/5q28d). Once a maximum tolerated dose (MTD) has been established, additional cohorts may be opened to refine dosing frequency optimization. Each cohort will include at least 3 participants and dosing of participants entering the study will be staggered by at least 5 days from D1 of previous patient for the first cohort only. Part 1 will include intra-patient dose escalation for 3 cycles, according to safety and tolerability parameters. The starting dose for Cycle 1 will be escalated in the next dose-escalation cohort until a cohort level starting dose-based MTD is reached. Individual patients may titrate above the starting dose-based MTD based on tolerability. Dose escalation cohorts will start with Cycle 1 at 12.5 µg GSK3745417. Within a cohort for an individual subject the dose may double for Cycle 2, and double again for Cycle 3 based on individual tolerability. The starting dose of subsequent cohorts will increase by 2-fold from Cycle 1 of the previous cohort. Patients may be dose reduced for subsequent cycles if there is lack of tolerability in the previous cycle (Section 6.4). The DLT period will be 28 days starting at Day 1 of Cycle 1 of each cohort. After 3 induction cycles, if a complete response (CR) or partial

response (PR) (IWG) is observed (See Appendix 9) each patient will continue with maintenance weekly dosing at the Cycle 3 dose level until disease progression or unacceptable toxicity. Participants with progressive disease after 3 induction cycles will be withdrawn from study. Participants with stable disease or PR after 3 cycles might receive additional cycles if the assessment by the investigator determined a benefit and GSK Medical Monitor agrees.

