# 1.1. Objectives, Estimands and Endpoints

Dose Escalation					
	Objectives	Endpoints			
Primary	To determine the safety, tolerability, and RP2D of a daily dosing schedule (induction) of GSK3745417	Frequency and severity of     Adverse Events (AEs), Serious     Adverse Events, (SAEs), Dose     Limiting Toxicity (DLT),     withdrawals due to AEs			
Secondary	To characterize the pharmacokinetics (PK) of GSK3745417, and relevant metabolites, as applicable, after single and repeat-dose administration.	GSK3745417 concentrations in plasma or PK parameters			
Exploratory					

Dose Escalation		
	Objectives	Endpoints
	CCI	

Estimands will not be considered for this first-time-in-human (FTIH) study.

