## 1.2. Study Design

Overview of Stu	udy Design and Key Features
Study intervention	• Part 1 will evaluate a dosing schedule of a 5 days on/2 days off schedule for 2 weeks, and then have an additional 2 weeks off dose for observation for a total of 28 days in each cycle (5 / 2 / 5 q28d). Once an MTD has been established, additional cohorts may be opened to refine dosing frequency optimization. Each cohort will include at least 3 participants. Part 1 will include intra-patient dose escalation for 3 cycles, according to safety and tolerability parameters. The starting dose for Cycle 1 will be escalated in the next dose escalation cohort until a cohort level MTD is reached.
	After 3 induction cycles, if a CR or PR (per appropriate response criteria) is observed, each patient will continue with maintenance weekly dosing at the Cycle 3 dose level until disease progression or unacceptable toxicity. Participants with progressive disease after 3 induction cycles will be withdrawn from study. Participants with stable disease or PR after 3 cycles might receive additional cycles.
Study	This is a FTIH, open-label, non-randomized study.
intervention	
Assignment	

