# 4.2.2. Main analytical approach

Adverse events analyses including the analysis of AEs, SAEs, and other significant AEs will be based on GSK Core Data Standards. Summary tables will focus on treatment-emergent AEs (TEAE) only. Details on treatment-emergent AEs are provided in Section 6.2.2. AEs will be coded using the standard MedDRA and grouped by system organ class

(SOC). AEs will be graded by the investigator according to the NCI-CTCAE (version 5.0).

A summary of treatment-emergent adverse events by system organ class and preferred term and maximum grade will be produced. A summary of common non-serious TEAEs that occurred in strictly 10% of the participants or above will be provided (no rounding for the percentage will be used in terms of 10% threshold, e.g., events with 9.9% incidence rate should not be included in this table). A summary of common (>=10%) TEAEs by overall frequency. The summary of common non-serious AEs will be grouped by SOC and PT. A summary of common adverse events by overall frequency will be produced.

The summary will use the following algorithms for counting the participant:

**Preferred term row**: Participants experiencing the same AE preferred term several times with different grades will only be counted once with the maximum grade.

**Any event row**: Each participant with at least one adverse event will be counted only once at the maximum grade no matter how many events they have.

The date of the first occurrence of an AE will be used to indicate which dose level an AE should be reported in.

A study treatment-related AE is defined as an AE for which the investigator classifies the relationship to study treatment as "Yes". A worst-case scenario approach will be taken to handle missing relatedness data, i.e., the summary table will include events with the relationship to study treatment as 'Yes' or missing. Study treatment-related AEs will be summarized by SOC, PT, and maximum grade. An overall frequency summary of non-serious drug related treatment emergent adverse events will also be produced.

Serious TEAEs will be summarized by SOC, PT, and maximum grade, as well as a separate summary of serious TEAEs by SOC and PT (Number of subjects and Occurrences). A separate summary of serious fatal and non-fatal drug-related treatment emergent by overall frequency will be created for disclosure requirements to regulatory agencies, displayed by PT.

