### 4.5.1. Extent of Exposure

Exposure to GSK3745417 will be summarized according to cumulative actual dose, number of cycles, time on study treatment (weeks) with separate sections for induction dosing and maintenance dosing in one table. Descriptive statistics including mean, median, standard deviation, minimum, and maximum will be calculated.

The cumulative dose, converted to and displayed in mg, is the sum of the actual dose administered in micrograms during each infusion for a subject throughout the study. For induction dosing, cumulative dose will be summarized by cycle. For induction cycles, the number of cycles will be calculated by the number of GSK3745417 doses received during the induction phase divided by 10. For subsequent maintenance cycles, the number cycles will be calculated by (last maintenance infusion date – first maintenance infusion date + 7)/28.

Subject level details for extent of exposure to study treatment will be listed. The listing will include cycle, total dose taken per cycle, cycle day, start and stop dates, scheduled dose, actual dose, and cumulative dose. Exposure data will be listed in both units (mg and  $\mu$ g).

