### 6.2.2.1. Treatment Emergent Flag for Adverse Events

Flag	Definition
Treatment Emergent	For AEs:  • Study Treatment Start Date ≤ AE Start Date ≤ Treatment Discontinuation Visit or Study Treatment Stop Date + 30 Days if TDV is missing  • AE Start Date is missing
	
 
For SAEs/AESIs:
 
Study Treatment Start Date ≤ AE Start Date or pre-existing (prior to exposure) AE Worsening Date ≤ Study Treatment Stop Date + 90 days or Start of Anti-Cancer Therapy, whichever occurs first
 
AE Start Date is missing
 

	Missing AE Start Date will be imputed following rules in Appendix 2 for determining Treatment Emergent AEs.

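### The SAP's adverse event tables count events that start on weekly maintenance in the same dose column as daily induction

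*SAP*

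**What the plan says.** The primary objective in SAP 1.1 names the daily schedule: "To determine the safety, tolerability, and RP2D of a daily dosing schedule (induction) of GSK3745417".

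SAP 1.2 describes what happens next to a Part 1 responder: "After 3 induction cycles, if a CR or PR (per appropriate response criteria) is observed", then "each patient will continue with maintenance weekly dosing at the Cycle 3 dose level until disease progression or unacceptable toxicity". Maintenance therefore differs from Cycle 3 in frequency but not in dose, and it has no fixed end.

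Four rules decide where an AE is counted:

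- SAP 4.1.1 sets the columns: "AE and PK related tables, listings and figures will be summarized by dose level".
- SAP 4.2.2 assigns an event to a column: "The date of the first occurrence of an AE will be used to indicate which dose level an AE should be reported in".
- SAP 6.2.2.1 ends the treatment-emergent window for AEs at "Treatment Discontinuation Visit or Study Treatment Stop Date + 30 Days if TDV is missing". Serious AEs and AEs of special interest run to 90 days after the last dose, or to new anti-cancer therapy if that comes first. Neither window is cut at the end of induction.
- No AE summary in SAP 4.2.2 or 4.3.2 is restricted to induction or split by phase.

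Exposure is handled differently. SAP 4.5.1 reports it "with separate sections for induction dosing and maintenance dosing in one table".

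**The concern.** Within one dose column the SAP cannot tell two schedules apart. A reader who takes the column as the safety of that dose given daily would also be reading events from weekly dosing, collected over a longer and open-ended time at risk. The tables give percentages of participants, so extra follow-up raises them even when the underlying rate is unchanged.

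The AE counts also cannot be matched to the exposure table, which does separate the phases. At stake is whether the AE, serious AE, treatment-related AE and special-interest tables describe the schedule named in the primary objective.

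**Working it through.** The SAP states no figure for this point, so there is none to reproduce. The check is a reading of the rules, then schedule arithmetic, then an illustration.

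**1. Does a maintenance event land in the induction column?** Take a participant whose Cycle 3 dose is D and who responds. Weekly dosing continues at D. A new AE begins on maintenance. It is treatment-emergent, because the participant is still on treatment. The dose in force at onset is D. Nothing else enters the column rule. The event is counted under D, beside participants who received D daily.

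**2. Schedule (SAP 1.2 and 4.5.1).**

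- Induction: 5 + 5 = 10 doses per 28 days.
- Maintenance: 28 / 7 = 4 doses per 28 days.
- Ratio: 10 / 4 = 2.5.

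**3. Time at risk at the Cycle 3 dose.** One cycle is 28 days. With m further 28-day periods it is 28 × (1 + m): 56, 112 or 196 days for m = 1, 3 or 6, which is 2, 4 or 7 times as long. These ratios leave out follow-up after the last dose. Add the 30 days of SAP 6.2.2.1 and let maintenance start on day 29, counted from Cycle 3 Day 1:

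- Without maintenance: 12 + 30 = 42 days.
- With maintenance: the last weekly dose falls on day 22 + 28m, so the window ends on day 52 + 28m, that is day 80, 136 or 220.
- Ratios to 42: 1.9, 3.2 and 5.2.

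**4. Illustration of the column percentage.** All inputs here are assumptions:

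- r = 0.20, the risk of at least one AE in one 28-day induction cycle.
- k, the hazard on maintenance relative to induction: 0.4 if it scales with dosing frequency (4 / 10), or 1 if unchanged.
- m = 1, 3 or 6.
- f, the share of the column that enters maintenance: 0.10 or 0.30. Protocol 9.1 uses these two values as response-rate hypotheses for Part 2. They are borrowed as a range and do not predict Part 1.

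Risk for one participant who enters maintenance: 1 − (1 − r)^(1 + k·m).

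Column percentage: (1 − f)·r + f·[1 − (1 − r)^(1 + k·m)].

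| k | m | One maintained participant | Column, f = 0.10 | Column, f = 0.30 |
|---|---|---|---|---|
| 0.4 | 1 | 26.8% | 20.7% | 22.0% |
| 0.4 | 3 | 38.8% | 21.9% | 25.6% |
| 0.4 | 6 | 53.2% | 23.3% | 30.0% |
| 1 | 1 | 36.0% | 21.6% | 24.8% |
| 1 | 3 | 59.0% | 23.9% | 31.7% |
| 1 | 6 | 79.0% | 25.9% | 37.7% |

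For example, with k = 1, m = 6 and f = 0.30: 1 − 0.8^7 = 0.790, and 0.7 × 0.20 + 0.3 × 0.790 = 0.377.

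The induction-only value is 20% throughout. The column therefore shows 20.7% to 37.7%, and exactly 20% if f = 0.

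**The case against.** The strongest reply is that little depends on these tables:

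- The maximum tolerated dose rests on dose-limiting toxicities through the N-CRM (Protocol 4.1). SAP 4.2.2 summarises those by cohort for the dose escalation period, not in the pooled columns.
- RP2D selection also draws on pharmacokinetic, pharmacodynamic and efficacy data.
- The study is terminated. SAP 1 and 4.8 leave a synoptic report on Part 1, with no interim analysis and no Part 2, and SAP 2 tests no hypothesis.
- Dose level is a natural column choice when participants change dose.
- AEs are listed by participant and the exposure listing carries dates, so a reader could separate the phases by hand.
- The output specification document, which is not among those supplied, might label weekly dosing separately.

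Most of this stands, and it lowers the importance of the point. It does not remove it. AEs and serious AEs are named in the primary endpoint alongside dose-limiting toxicities. The SAP requires no phase split, and a listing is not a summary.

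Three stronger readings are tempting, and the documents do not support them:

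- A reader might infer that the RP2D or the whole primary objective is confounded. The handling of dose-limiting toxicities rules that out.
- A reader might infer a built-in false dose-toxicity gradient, because Cycle 3 carries each participant's highest dose. Escalation is only permitted: "Within a cohort for an individual subject the dose may double for Cycle 2, and double again for Cycle 3 based on individual tolerability". Reductions are allowed too, and someone who is never escalated spends all three cycles at one dose. A gradient is possible, not established.
- A reader might quote the one-participant risks (up to 79%) as the distortion. They apply only to someone who enters maintenance and are not column percentages.

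Repeat events limit the effect further. Each preferred term counts once per participant, so a recurrence on maintenance adds nothing to its row at that dose unless its grade is higher.

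**Conclusion.** The point holds in a limited form. As written, the SAP counts maintenance-onset AEs, serious AEs and AEs of special interest in the column for daily induction at the same dose, while the primary objective concerns the daily schedule. The DLT summary is not affected in this way.

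The size cannot be fixed from the documents, because the number who reached maintenance is not given. It is zero if nobody did. Otherwise an assumed 20% would appear as about 21% to 38% over the range shown, which rests on a constant hazard, k between 0.4 and 1, one to six periods of maintenance, and 10% to 30% of the column entering. With a small share entering and a hazard that falls with dosing frequency, the shift is only a few points.

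This is a worthwhile, inexpensive correction to descriptive safety tables. It is not a must-fix.

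**What to change.** In SAP 4.1.1, 4.2.2 and 4.3.2:

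- Derive a phase flag (induction or maintenance) from the dosing dates.
- Present the AE, serious AE, treatment-related AE and special-interest summaries by dose level for induction, with maintenance-onset events in a separate section, matching SAP 4.5.1.
- Use one induction window for everyone: first dose to the earlier of the first maintenance dose or the last induction dose + 30 days. Without this cap, induction would end at the first maintenance dose for responders but 30 or 90 days after the last dose for others. A small difference remains: if maintenance starts on day 29 of Cycle 3, it cuts the window 29 − 12 = 17 days after the last induction dose, instead of 30.
- State where to show treatment-emergent events that fall after this window in participants never on maintenance, so that no serious AE or special-interest event drops out.
- Show participants and participant-time for each column.

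The cost is SAP wording and one derived flag. Dosing dates are already collected, and no new data are needed. The downside is sparser columns, with about 22 participants planned for Part 1. If nobody reached maintenance, one sentence saying so is enough.

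The change does not separate Cycle 1, 2 and 3 participants from different cohorts who share a dose column. That mixing comes from intra-patient escalation and would need its own display or a caveat.

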## 6.4.1.1. Intra-Patient Dose Escalation

Intra-patient dose escalation is permitted for induction treatment cycles 2 and 3 depending on safety and tolerability of the first dosing cycle. To allow intra patient dose escalation for the next dosing cycle:

- Investigator and MM must both consider that dose escalation is in the best interests of the participant
- Participant must have received at least 7 of the 10 doses in the prior cycle
- Participant must not have experienced:
  - Any Grade  $\geq$ 3 AE
  - $\circ$  Grade  $\geq$ 3 TLS
  - A DLT (which includes Grade 3 CRS, all non-hematologic Grade 3 events with a few exceptions as per Table 7)
  - More than 1 episode of Grade 2 CRS in the previous cycle
  - Evidence of ongoing immune activation during the observation period (sustained or intermittent Grade ≥2 fever ongoing after the first week of the observation period)

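### Induction AE tables by dose level mix participants who started at a dose with those titrated into it after a cycle free of Grade 3 or higher AEs, so a column rate is not the rate for first treatment at that dose

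*SAP*

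**What the plan says.** - SAP 4.1.1, on the Safety Analysis Set: "AE and PK related tables, listings and figures will be summarized by dose level". The next sentence groups other displays differently: "Study population and efficacy tables and listings will be summarized by treatment sequence".
- SAP 4.2.2 assigns events to columns by onset: "The date of the first occurrence of an AE will be used to indicate which dose level an AE should be reported in". It plans tables of AEs, treatment-related AEs and serious AEs by maximum grade. DLTs alone are summarised by cohort.
- SAP 1.1 gives the primary objective these tables serve: "To determine the safety, tolerability, and RP2D of a daily dosing schedule (induction) of GSK3745417". Frequency and severity of AEs and SAEs are named in its endpoint.
- Protocol synopsis, Overall Design: "Within a cohort for an individual subject the dose may double for Cycle 2, and double again for Cycle 3 based on individual tolerability", and "The starting dose of subsequent cohorts will increase by 2-fold from Cycle 1 of the previous cohort".
- Protocol 6.4.1.1: "Intra-patient dose escalation is permitted for induction treatment cycles 2 and 3 depending on safety and tolerability of the first dosing cycle". Among the events that bar titration is "Any Grade $\geq$ 3 AE". A DLT, Grade 3 or higher TLS, more than one Grade 2 CRS episode in the previous cycle, ongoing immune activation, or fewer than 7 of 10 doses received also bar it. Section 4.1.2 carries essentially the same list.

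**The concern.** Titration steps and cohort steps are both two-fold, so a titrated participant lands on the starting dose of a later cohort. A column above 12.5 µg can then hold two kinds of participant: those first treated at that dose, and those who reached it because they had no Grade 3 or higher AE at a lower one. Entry of the second kind depends on the outcome being counted. The same person can appear in up to three columns.

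A reader of a Phase 1 AE table will take the 50 µg column as what to expect when a participant is started at 50 µg. The pooled rate does not estimate that. It mixes first-exposure toxicity, toxicity in people selected for tolerance, and any accumulation from earlier cycles, and the reader cannot separate them. At stake is the AE and SAE part of the primary safety result, and any statement on the tolerability of a starting dose drawn from it. The point concerns induction only.

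**Working it through.** The plan states no figure for this, so there is nothing to reproduce. The check has three steps.

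**1. Who is in each column.** Inputs: cohorts of 3 (the minimum in SAP 1.2), two-fold starting doses, up to two doublings, everyone titrated.

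| Column | Starters (Cycle 1) | Titrated, Cycle 2 | Titrated, Cycle 3 | Titrated share |
|---|---|---|---|---|
| 12.5 µg | 3 | 0 | 0 | 0/3 |
| 25 µg | 3 | up to 3 | 0 | up to 3/6 = 50% |
| 50 µg | 3 | up to 3 | up to 3 | up to 6/9 = 67% |
| Above highest starting dose | 0 | some | some | 100% |

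**2. Effect of selection alone.** Let p_d(b) be the chance of a Grade 3 or higher AE in a cycle at dose d for a participant with susceptibility b. A starter's rate is E[p_d(b)]. After one event-free cycle at the dose below, d′, the rate is

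E[p_d(b)(1 − p_d′(b))] / E[1 − p_d′(b)].

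Both p_d and p_d′ rise with b, so this is at most E[p_d(b)], with equality only if participants do not differ in b. The column rate is total events divided by total participants exposed at that dose.

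The documents give neither AE rates nor heterogeneity, so these are assumptions: starter rates of 10, 20, 33, 50 and 60% at 12.5, 25, 50, 100 and 200 µg; cohorts starting at 12.5 to 100 µg; a logistic model with a normal random intercept of variance σ²; latent correlation ρ = σ²/(σ² + π²/3). Participants who are not titrated contribute no further cycles.

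| ρ | 50 µg column (starters 33%) | Gap | 100 µg column (starters 50%) | Gap |
|---|---|---|---|---|
| 0 | 33.0% | 0 | 50.0% | 0 |
| 0.05 | 32.4% | −0.6 | 49.1% | −0.9 |
| 0.2 | 31.0% | −2.0 | 46.6% | −3.4 |
| 0.35 | 29.4% | −3.6 | 44.5% | −5.5 |
| 0.5 | 27.9% | −5.1 | 42.4% | −7.6 |

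Numerical integration of the same model agrees with these simulated rates to within about 0.1 point.

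As a second curve, take the N-CRM prior means in Protocol 9.2 (α = −1.7907, ln β = 0.1961, reference dose 50 µg) as a proxy for the starter rate. At 100 µg, logit p = −1.7907 + e^0.1961 × ln 2 = −1.7907 + 1.2166 × 0.6931 = −0.947, so p = 27.9%. With cohorts starting at every dose from 12.5 to 200 µg, the pooled 100 µg column reads 27.9%, 26.2% and 23.7% for a random-intercept SD of 0, 1 and 2, a gap of 0 to 4.2 points.

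**3. Add carry-over.** Protocol 4.4.2 says preliminary non-clinical data suggest cytokine symptoms or immune activation may accumulate with daily dosing, without a figure. Multiply the odds of an event by an assumed ratio for each earlier cycle, in the model of step 2:

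| ρ | Odds ratio per earlier cycle | 50 µg (33%) | Gap | 100 µg (50%) | Gap |
|---|---|---|---|---|---|
| 0.5 | 1.5 | 32.9% | −0.1 | 47.8% | −2.2 |
| 0.5 | 2 | 36.6% | +3.6 | 51.5% | +1.5 |
| 0.2 | 1.5 | 37.6% | +4.6 | 53.2% | +3.2 |

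Modest carry-over cancels or reverses the selection effect. The first-occurrence rule in SAP 4.2.2 is not modelled. Where an event starts at a low dose and recurs after titration, that rule may leave it in the lower column only, a further downward push.

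**The case against.** The strongest reply has five parts.

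- **The direction is not established.** A reader might infer that toxicity at higher doses is understated. Step 3 shows that the documents do not support this: the sign depends on heterogeneity and carry-over, and the documents quantify neither. This stands in full.
- **The largest gap is not a pooling effect.** In the model of step 2 at ρ = 0.5, the 200 µg column reads 40.5% against 60% for a starter, and a reader might infer a 19-point error or a reversed dose relation. No modelled cohort starts at 200 µg, so that column is 100% titrated. Nothing is pooled there and a split would not change it. It needs a label.
- **The SAP makes no comparison between columns.** It plans no test and states no independence assumption, and display details sit in a separate Output and Specification document not available here. So one cannot say that the plan treats columns as separate groups, or that footnotes and denominators are missing from it altogether. That stands. Even so, side-by-side percentages by dose invite a dose-response reading, and the SAP text specifies no split and no caveat.
- **Little depends on these tables.** Escalation and MTD use the N-CRM on DLTs, DLTs are shown by cohort, the RP2D draws on all available data, and the study was terminated with Part 2 cancelled. This limits the consequence. It does not correct a table that remains a main Part 1 result, and the DLT display does not cover AE and SAE frequency and severity.
- **The data can be traced, and the split is imprecise.** Listings give each AE by participant, and exposure by cycle and dose. One event in 3 starters has an exact 95% interval of 0.8 to 91%; 3 in 9 pooled has 7 to 70%. Both dwarf a gap of 0 to 8 points. The split therefore adds no precision. Its gain is a count with a defined meaning, which readers would otherwise have to rebuild by hand.

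**Conclusion.** The point holds as one about interpretation. Dose columns above 12.5 µg can mix unselected first exposures with participants selected on the tabulated outcome, up to half the column at 25 µg and two thirds at 50 µg with cohorts of 3 and full titration. The pooled rate is then not the rate for a participant first treated at that dose. Selection alone lowers it by about 0 to 5 points at 50 µg and 0 to 8 points at 100 µg for assumed correlations of 0 to 0.5. Carry-over pushes the other way, so the net direction is unknown. These sizes rest on assumed AE rates, correlations and odds ratios. The composition counts and the titration conditions come from the documents. The change is worth making because Cycle 1 events by starting dose are free of both selection and carry-over, whatever the sign.

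**What to change.** In SAP 4.1.1 and 4.2.2, for the induction AE, SAE and treatment-related AE tables by maximum grade, add:

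- **(a)** Cycle 1 events by starting dose, with the number starting at that dose as denominator;
- **(b)** events in Cycle 2 or 3 among participants titrated to that dose, with the number titrated as denominator.

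Label (b), and any column with no starters, as participants selected for tolerating the lower dose. Rest statements on the tolerability of a starting dose on (a). Keep the pooled column as a total, and note that (a) and (b) need not add up to it, because participants who stay at a dose or are reduced to it in Cycle 2 or 3 fall in neither.

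The cost is SAP wording and extra columns or one extra table. The data are already collected, and treatment sequence is already a grouping in SAP 4.1.1. The downside is small cells, about 3 per starting dose, so these should be read as counts rather than precise rates. No dose or titration rule changes.
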